#### 4.0 Study Intervention(s)/Investigational Agent(s)

4.1 Description:

Mindful Breathing Training (MBT): All participants will undergo mindful breathing training (MBT). MBT is a mindfulness-based intervention that guides participants to pay attention to the present experience. Participants will be trained to become aware of mind-wandering, disengage, and shift attention back to the present experience. Participants will practice mindful breathing using a computerized application that they will be able to access on the web. This training will be administered through a University of Minnesota server on an internet browser (e.g., Google Chrome). During this task, participants will close their eyes and focus on their breath, tapping at the end of each breath. Participants will first complete five sessions (for 10, 12.5, 15, 17.5, and 20 minutes) of mindful breathing training at home using a personal laptop, tablet, or cell phone over five days. Following this training, participants will be randomized to undergo either ten 20-minute sessions of active or sham tDCS concurrent with MBT across two weeks in lab. Participants are not required to complete all five mindful breathing sessions prior to starting in-person treatment. Following lab MBT training with either active or sham tDCS, participants will complete 15 sessions of MBT training across three weeks at home or inperson.

**tDCS**: We will use transcranial direct current stimulation (tDCS), a noninvasive brain stimulation technique that can modulate brain activity and connectivity, to stimulate the dorsolateral prefrontal cortex (DLPFC). Weak electrical current (~2mA) is applied to the scalp using anodal and cathodal

electrode sponges, which increase or decrease cortical excitability respectively. Research has shown in both healthy participants and patients (e.g. Alzheimer's disease, Parkinson's disease, and depression) that tDCS has the potential to modulate synaptic strengthening and neurotransmitter-dependent plasticity underlying changes in behavior and learning (Lang et al., 2005). Sham stimulation will serve as a control condition with current applied only for the first and last 30 seconds of the 20-minute session.

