#### VERSION DATE: 03/11/2021

Figure 1

5.2 Study Procedures: Participants will complete a baseline assessment (including a diagnostic interview, clinical assessments, behavioral tasks, questionnaires, an EEG/ECG visit, and an optional MRI scan) prior to intervention, an interim assessment (clinical assessments and questionnaires) after 5 intervention sessions, a post-intervention assessment (including clinical assessments, behavioral tasks, questionnaires, an EEG/ECG session, and an optional MRI scan) after the tDCS intervention, and a final assessment (clinical

assessments, behavioral tasks, questionnaires, and an EEG/ECG session) following the at-home/in-person MBT intervention. The intervention will consist of MBT completed at home or in-person and MBT completed in the laboratory concurrent with active or sham tDCS (see Figure 1 and Table 1 for an outline of study activities). All self-report questionnaires will be administered online through REDCap, a HIPAA-compliant survey system, or on paper. All online selfreport questionnaires administered through REDCap will be completed by participants either in-person or remotely. Participants who are unable to complete all online self-report questionnaires in-person due to time constraints will be emailed an access code for each questionnaire and a link to the REDCap website. Upon opening the website link, they will be prompted to enter their access code in order to fill out questionnaires. Questionnaires administered on paper will be entered into REDCap by research staff.

Remote Conduct of Study Procedures- In the interest of disease containment and prevention, study staff will use HIPAA-compliant communication platforms approved for use at the University of Minnesota (e.g., Zoom) at their discretion to conduct necessary study procedures when possible during the period of heightened public health concern due to COVID-19. This will allow for participants to be given the option for remote study visits when deemed necessary by either the participant or by research staff.

Week		1	1, 5, and 9	1 and 5	3-4	3	5	9
	Time	Baseline Assessment	EEG 1, 2, & 3	MRI 1 & 2	tDCS + MBT Visits 1- 10	Interim Assessment	Post-tDCS Assessment	Final Assessment
Consent		Х						
tDCS Safety Screen		Х						
MINI	20 min	Х						
MINI Depression Module							Х	Х
MADRS-S		Х				X	Х	Х
C-SSRS (LV or SLV)		Х				X	Х	Х
MAAS		Х				X	Х	Х
FMI		Х				Х	Х	Х
RSS		Х					Х	Х
IDAS-II		Х						
DAS		Х					Х	Х
DERS		Х					Х	Х
AAQ-II		Х					Х	Х

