#### • Mindful Breathing Training Description

30 sessions of MBT: Participants will be instructed to practice mindfulness and will complete a guided computerized task. During the computerized task, they will be asked to focus on the sensations of their breaths. They will tap at the end of each breath and receive feedback. Participants will be trained to use the mindful breathing program after their last in-person baseline visit. Training will involve a brief overview of mindful breathing and a one-minute training to introduce the task. The first 5 sessions will be competed at home for 10, 12.5, 15, 17.5, and 20 minutes respectively. The first session may be completed in person during the mindful breathing training to ensure participants understand how to use the training program. Participants are not required to complete all five breathing sessions prior to starting in-person treatment. The next 10 sessions will last 22 minutes and will be done concurrent with active or sham tDCS. The remaining 15 sessions will last 20 minutes and participants will be given the option of completing these either in-person (only if the study team determines that it would be helpful for the participant to complete these sessions in-person) or at home using a personal laptop, tablet, or cell phone. This app will collect data about the quality of focus during MBT and session completion information. See Figure 1.

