- Participants will then be randomly assigned to one of two conditions: active tDCS + MBT and sham tDCS + MBT. Participants will undergo 10 daily sessions of tDCS across two weeks (visits 4-13). Missed sessions may be rescheduled. If there is a month or longer delay between the last baseline assessment visit (e.g.,

initial assessment, EEG, or MRI), participants may be asked to repeat some or all of the baseline research visits and will be paid accordingly.

- 4) Following the treatment, participants will complete a post-tDCS MRI scan, EEG/ECG session, and assessment visits (visit 14-16) that will include behavioral and cognitive assessments as well as questionnaires.
- 5) Participants will then complete 15 sessions of MBT either at home or in-person (only if the study team determines that it would be helpful for the participant to complete these sessions in-person) across 3 weeks. After they complete the home-based MBT training, all participants will complete a final EEG/ECG session and final assessment (visits 17 and 18), irrespective of how many athome/in-person MBT sessions were completed.

In total, this study will require 18 in-person visits and 20 online MBT sessions that can be completed at home (see Figure 1 for an overview of study activities). For participants who complete the 3-weeks of MBT in-person, there will be an addition of 15 in-person visits and a total of 4 online MBT sessions.

**Randomization:** A randomized block design will be used to assign each subject to undergo either active or sham tDCS in a 1:1 ratio. Randomization will occur after completion of the 5 at-home MBT sessions before their first tDCS + MBT laboratory visit.

5.4 Study Duration: The total duration of research activities for individual participants will involve 18 in-person visits and 20 MBT sessions that can be completed at home or in person (only if the study team determines that it would be helpful for the participant to complete these sessions in-person). Research-related activities will occur over the duration of up to 10 weeks.

The anticipated duration to complete all study-related activities, include data analysis and publications is 4 years (present to 2022). It is anticipated that year 1 and year 2 will involve data collection and year 3 and 4 will involve data analysis, presentations, and publications.,

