# MRI Exclusion Criteria: If participants meet MRI exclusion criteria, they may not participate in the MRI scan but may still choose to participate in other study visits

 Participants with conductive, ferromagnetic, or other magnetic-sensitive metals implanted in the head excluding the mouth that cannot safely be removed. Examples include cochlear implants, implanted electrodes/stimulators, aneurysm clips or coils, stents, bullet fragments, jewelry and hair barrettes

8.3 Screening: Potential participants (if age 18 or older) or parents of potential participants (if under age 18) will first complete an initial, brief telephone interview with a member of the research team. Prior to the phone screen, potential participants will be informed that they will need to fill out a short online survey to determine their eligibility and so they would need email access during the phone call. During the phone call, the study will be explained to the participant and/or their parent and will include questions about the participant's medical history, their mood, and behavior. A REDCap survey link for the MADRS-S, a depression rating scale, will be emailed to potential participants or to parents of potential participants during the phone call. The phone screen MADRS-S will not include item 9 ("Zest for life") in order to reduce any risk of triggering suicidal thoughts or ideation. The phone screen and MADRS-S will serve to select participants likely to meet inclusion criteria and to screen out

participants who meet exclusionary criteria. The REDCap survey will be linked to a dummy ID that will not be attached to a name. Potential participants/parents will be told that it is recommended that they/their child fill out their responses while the study staff remains on the phone. The survey will take about 3 to 5 minutes to complete. Participants who are interested in continuing with the study and who have a score of 13 or more on the MADRS-S will be eligible to schedule in-person visits. Participants or parents (if under age 18) will provide verbal consent for the screen to be completed. See the attached phone screen. Participants may also be screened using a REDCap survey that the participant (if age 18 or older) or parent will complete.

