Since we do not have pilot data with adolescents using either of these interventions, we were unable to conduct a power analysis to calculate an appropriate sample size. Budget and time constraints necessitate a relatively small sample size. While some studies in the literature have reported significant effects using similarly small samples, we cannot be certain that the study is powered appropriately to confirm or refute our hypotheses. Therefore, we have framed the project with a primary goal of establishing feasibility (our ability to recruit, adolescents' acceptance of randomization, adolescents' tolerability of the interventions) and of collecting data that will allow a power calculation to determine the sample size necessary for the federal grant to follow this work.

15.3 Statistical Analysis: A p-value of .05 will be used to determine significance for behavioral measures and a p-value of .005 will be used to determine significance for neuroimaging measures. Paired t-tests will be used to compare baseline versus post-tDCS and post-MBT intervention for both intervention groups for biological, clinical, and behavioral measures. Between-group t-tests will be conducted on the side-effects to examine group differences in prevalence of side effects. Feasibility will be determined by looking at descriptive statistics about enrollment and eligibility of people that express interest in the study and enroll as well as retention of enrolled participants. Correlation analysis will be conducted to assess how changes in clinical and behavioral relate to biological measures following intervention. Mixed repeated measures ANOVAs will test our hypothesis that the active tDCS group will show greater change than the sham tDCS group with condition (active or sham) as the between participant measures; within-participant measures will include behavioral.

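### No MADRS-S is scheduled between the week-1 baseline and the fifth tDCS session, so the active-sham comparison may lose some precision

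*Combined protocol and SAP*

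**What the plan says.** - **Order of events.** Section 5.2 (Mindful Breathing Training Description) starts MBT once the baseline visits are over: "Participants will be trained to use the mindful breathing program after their last in-person baseline visit". Section 4.1 describes five sessions "of mindful breathing training at home using a personal laptop, tablet, or cell phone over five days" and continues: "Following this training, participants will be randomized". Section 5.3 then states: "Randomization will occur after completion of the 5 at-home MBT sessions before their first tDCS + MBT laboratory visit".
- **MADRS-S schedule.** The table in section 5.2 places it at baseline (week 1), interim (week 3, after five intervention sessions), post-tDCS (week 5) and final (week 9). The tDCS visits are in weeks 3-4. Under Clinical Assessments, further MADRS-S measurements are allowed only for a clinical reason.
- **Delay rule.** Section 5.3 has a provision that begins "If there is a month or longer delay between the last baseline assessment visit". Repeating the visits is then optional and may cover only some of them.
- **Analysis.** Section 15.1 plans repeated measures ANOVA of condition on MADRS-S before and after intervention. Section 15.3 adds: "Paired t-tests will be used to compare baseline versus post-tDCS and post-MBT intervention for both intervention groups". The only covariate mentioned is the number of visits completed. No model adjusts for the baseline score.
- **Status of the outcome.** Section 3.1 lists change in depression symptoms as a primary clinical outcome, and Aim 3 asks whether tDCS enhances MBT. Section 15.2 says that the data will feed the power calculation for the next grant.

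**The concern.** By the time a participant is allocated, the week-1 score is about two weeks old and predates five sessions of a treatment that both arms receive. Depression scores fluctuate, so an older score will plausibly predict the post-tDCS score less well than one taken just before stimulation. With about 15 per arm, any avoidable noise in the reference score widens an interval that is already wide.

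The delay rule does not close the gap. It counts from the last baseline visit, whereas the MADRS-S belongs to the first. A score can therefore be more than a month old without triggering the rule, and when the rule does apply the MADRS-S need not be among the measures repeated.

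The within-arm paired tests raise a separate issue. The week-1 score is also an eligibility score (13 or more), so change from week 1 contains three things: regression to the mean, any run-in MBT effect, and the tDCS phase. The same applies to the response measure of at least 50% reduction if it is referred to week 1; the protocol does not name the reference score.

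**Working it through.** The plan states no power, SD, target difference or pre-post correlation (section 15.2), so there is no figure of its own to reproduce.

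**Timing, from the week labels.** Baseline (week 1) to first tDCS (week 3) is about 2 weeks. Baseline to post-tDCS (week 5) is about 4 weeks, against about 2 weeks from a score taken at randomisation.

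**Precision of the arm comparison.** Inputs: 15 per arm (section 5.1), and two-sided alpha of 0.05 (section 15.3; two-sided is assumed). Units are the MADRS-S SD, assumed equal at each time. Let ρ be the correlation of the pre-treatment score with the week-5 score.

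- A repeated measures ANOVA with two time points is a t-test on change, with variance 2(1 − ρ).
- ANCOVA has variance 1 − ρ².
- The SE of the arm difference is √variance × √(2/15).

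Assume ρ = 0.5 for the week-1 score. For a score taken at randomisation:

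| Assumed ρ, new score | Change variance (SE) | Fall | ANCOVA variance (SE) | Fall |
|---|---|---|---|---|
| 0.5 (no decay) | 1.00 (0.365) | 0% | 0.75 (0.316) | 0% |
| 0.6 | 0.80 (0.327) | 20% | 0.64 (0.292) | 15% |
| 0.7 | 0.60 (0.283) | 40% | 0.51 (0.261) | 32% |

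The ANCOVA falls are 1 − 0.64/0.75 = 1 − 0.853 and 1 − 0.51/0.75 = 1 − 0.680. As equivalent totals, 30/0.853 = 35.2 and 30/0.680 = 44.1 participants instead of 30. The interval narrows by less: √0.853 = 0.924, or about 8%, and √0.680 = 0.825, or about 17%.

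**Which part comes from what.** At ρ = 0.5, moving from change scores to ANCOVA on the existing week-1 score already cuts variance from 1.00 to 0.75. The new score is responsible only for the further step to 0.64 or 0.51.

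**Effect of the entry cut.** Selecting on the week-1 score narrows its spread, which reduces the penalty for change scores. In a simulation of 0.5 against 0.6, the old-to-new ratio of change variance fell from 1.25 to 1.14-1.16 with the cut 1 SD below the mean, and to 1.06-1.09 with the cut at the mean. The saving is then about 6% (1 − 1/1.06) to 14% (1 − 1/1.16), not 20%. The ANCOVA ratio, 1.17 without a cut, was 1.18-1.20 with one. The direction did not reverse in any case run.

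**Within-arm change.** In the same simulations, now over all the correlation sets run and with no treatment effect at all, the mean score fell by 0.06 to 0.32 SD between week 1 and the start of tDCS. This is regression to the mean alone. It depends on where the cut lies in the distribution, which the documents do not show.

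**The case against.** A reader might infer that the estimated tDCS effect is biased. The documents do not support that. The run-in is common to both arms and precedes randomisation, so the active-sham contrast is fair on either score.

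A reader might also call week 1 the only pre-treatment score. It is not: section 8.3 requires a screening MADRS-S of 13 or more, without item 9, before in-person visits are scheduled. Some regression to the mean may thus have occurred before week 1, and the simulated falls, which use a single cut, may be too large.

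It is tempting to let the new score replace week 1 altogether. That would do harm. Rumination, emotion regulation, mindfulness, EEG, MRI and cortisol are all measured before MBT, and section 15.1 correlates symptom change with change in several of them; the windows would no longer match. MBT is itself a study treatment, so for total change a score before any MBT is the right reference. The protocol does not claim that the paired tests isolate tDCS.

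The gain rests on assumed correlations and is zero without decay. ANCOVA on the existing score is worth more at ρ = 0.5 than the step to 0.6. Section 15.2 also puts feasibility first and admits uncertain power. All of this stands and limits the point. It does not remove it, because the symptom data are meant to inform the next trial's sample size.

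The cost is not quite nil. The statement "The survey will take about 3 to 5 minutes to complete" describes the screening form without item 9. The tDCS visit is headed 45 minutes, but its parts add to 20 + 22 + 5 = 47.

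**Conclusion.** The gap in the schedule is plain from the text, and the repeats that the protocol allows do not reliably fill it. The consequence for the arm comparison is a possible loss of precision, with no bias. Under assumed correlations of 0.5 for the old score and 0.5 to 0.7 for a new one, the avoidable variance is 0% to 32% with baseline adjustment. It is 0% to 40% for unadjusted change, and less after the entry cut. These figures assume equal SDs at each time and cannot be firmed up from the documents. Within-arm change from week 1 remains valid as total change, but it should not be read as the effect of the tDCS phase. This is a worthwhile, inexpensive improvement to a feasibility trial; the planned comparison is valid without it.

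**What to change.** 1. Add a full MADRS-S to the schedule after the MBT run-in and before randomisation or, at the latest, before the first stimulation while blinded. Before randomisation is better, because a visit-1 score would be missing for anyone allocated who never attends. Section 5.2 already allows remote REDCap completion, so no visit is added and the full tDCS visit is not lengthened.
2. Compare post-tDCS MADRS-S between arms by ANCOVA with this score as covariate, optionally with the week-1 score too. For participants already past this point, adjust for the week-1 score, and fix in advance how the two groups are combined.
3. Keep the week-1 score for eligibility, for total within-arm change including run-in MBT, and for correlations with the other week-1 measures. Report within-arm change from the new score beside it, and name the reference score for response.
4. Reconcile section 5.3, which places randomisation after all five home sessions, with sections 4.1 and 5.2, which do not require all five before in-person treatment. This decides what the run-in is when the new score is taken.

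Cost: one schedule entry, a few minutes per participant, and staff review of item 9 answers under the existing safety monitoring.

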#### 4.2 Drug/Device Handling:

- tDCS will be applied with a StarStim Enobio system (Neuroelectrics, Barcelona, Spain) using a bipolar stimulation montage.
- This device has been approved for use in research without an investigational device exemption due to meeting criteria for non-significant risk (NSR).
- In addition, the device has built in safety mechanisms which allow for the immediate cessation of stimulation should the participant become uncomfortable or if the impedance of the stimulation electrodes is too high.
- The current will be administered via two saline soaked electrode sponges during each intervention session, using a current strength of 2.0 mA.
- These administration procedures are in line with other protocols that have outlined the safe use of tDCS in pediatric populations (Krishnan et al., 2015).
- The tDCS cap and stimulation electrodes/sponges will be washed and disinfected after each intervention session and stored under lock and key in [name].
- 4.3 Biosafety: N/A IND/IDE

#### 5.0 Procedures Involved

5.1 Study Design: Participants will undergo ten daily sessions of one of two conditions: 1) active tDCS + Mindful Breathing Training or 2) sham tDCS + Mindful Breathing Training (approximate final n of 15 per group). A randomized block design will be used to assign each subject to a condition (sham or active tDCS). This study will be double-blind to +/- tDCS stimulation.

#### VERSION DATE: 03/11/2021

Figure 1

5.2 Study Procedures: Participants will complete a baseline assessment (including a diagnostic interview, clinical assessments, behavioral tasks, questionnaires, an EEG/ECG visit, and an optional MRI scan) prior to intervention, an interim assessment (clinical assessments and questionnaires) after 5 intervention sessions, a post-intervention assessment (including clinical assessments, behavioral tasks, questionnaires, an EEG/ECG session, and an optional MRI scan) after the tDCS intervention, and a final assessment (clinical

assessments, behavioral tasks, questionnaires, and an EEG/ECG session) following the at-home/in-person MBT intervention. The intervention will consist of MBT completed at home or in-person and MBT completed in the laboratory concurrent with active or sham tDCS (see Figure 1 and Table 1 for an outline of study activities). All self-report questionnaires will be administered online through REDCap, a HIPAA-compliant survey system, or on paper. All online selfreport questionnaires administered through REDCap will be completed by participants either in-person or remotely. Participants who are unable to complete all online self-report questionnaires in-person due to time constraints will be emailed an access code for each questionnaire and a link to the REDCap website. Upon opening the website link, they will be prompted to enter their access code in order to fill out questionnaires. Questionnaires administered on paper will be entered into REDCap by research staff.

Remote Conduct of Study Procedures- In the interest of disease containment and prevention, study staff will use HIPAA-compliant communication platforms approved for use at the University of Minnesota (e.g., Zoom) at their discretion to conduct necessary study procedures when possible during the period of heightened public health concern due to COVID-19. This will allow for participants to be given the option for remote study visits when deemed necessary by either the participant or by research staff.

Week		1	1, 5, and 9	1 and 5	3-4	3	5	9
	Time	Baseline Assessment	EEG 1, 2, & 3	MRI 1 & 2	tDCS + MBT Visits 1- 10	Interim Assessment	Post-tDCS Assessment	Final Assessment
Consent		Х						
tDCS Safety Screen		Х						
MINI	20 min	Х						
MINI Depression Module							Х	Х
MADRS-S		Х				X	Х	Х
C-SSRS (LV or SLV)		Х				X	Х	Х
MAAS		Х				X	Х	Х
FMI		Х				Х	Х	Х
RSS		Х					Х	Х
IDAS-II		Х						
DAS		Х					Х	Х
DERS		Х					Х	Х
AAQ-II		Х					Х	Х
Cash Choise Task		Х					Х	Х
Side Effects Questionnaire					Х			
tDCS Perceptions Questionnaire		Х					Х	Х
PSQI		Х					Х	Х
CRT	20 min	Х					Х	Х
Rest Eyes Open/closed + ECG	6 min		Х					
Rumination	3 min		Х					
Distraction	3 min		Х					
Mindful Breathing + ECG	10 min		X (only EEG					

